11.6 Stopping Rules

There is not planned interim analysis for efficacy.

11.6.1 Death possibly, probably to definitely related to CSA: Any death in the Neoral group that is assessed as at least possibly related to Neoral will result in a pause to study accrual and a review by the DSMB.

11.6.2 Targeted Toxicities: Other expected toxicities will be continuously monitored using the method of Ivanova et al [Ivanova, A., Qaqish, B.F., and Schell, M.J. (2005). Continuous toxicity monitoring in phase II trials in oncology. *Biometrics* 61: 540-545.]. The method generates a Pocock-type boundary for repeated testing for toxicity. This is a Pocock-type stopping boundary that yields the probability of crossing the boundary at most 5% when the rate of grade 3 or greater target toxicity is equal to the acceptable rate of 20%. The method will stop the trial early with 40% and 86% probability if the toxicity rate is 30% or 40%, respectively.

11.6.3 Data Safety Monitoring Board (DSMB): The conduct of this study will be overseen by a DSMB of 3 experts who are not participating in this study. The DSMB will be responsible for recommendations to the Principal Investigator regarding possible trial closure and/or early reporting of the study. The study team (with the exception of the study statistician) will not have access to the summary outcome data until released by the DSMB.

Table 4. Toxicity monitoring boundaries. The following table will be used. Targeted toxicities include renal dysfunction, hypertension and liver toxicity. The trial will be paused and reported to the DSMB if the number of patients with grade 3 or greater AE's for any of the targeted toxicities is equal to or exceeds b_n out of n patients with completed follow-up (Day 7).

Number of Patients, n	1	2	3	4	5	6	7	8	9	10	11	12	13	14	15	16	17	18	19	20
Boundary, b_n	-	-	3	4	4	5	5	5	6	6	6	7	7	7	8	8	8	9	9	9
Number of Patients, n	21	22	23	24	25	26	27	28	29	30	31	32	33	34	35	36	37	38	39	40
Boundary, b_n	10	10	10	11	11	11	12	12	12	13	13	13	13	14	14	14	14	15	15	15
Number of Patients, n	41	42	43	44	45	46	47	48	49	50										
Boundary, b_n	15	16	16	16	16	17	17	17	17	18										

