3. PATIENT SELECTION

3.1 Eligibility Criteria

- 3.1.1 Laboratory-confirmed SARS-CoV-2 infection within the past 10 days.
- 3.1.2 Patients admitted to non-ICU hospital floors or in an emergency department awaiting admission to a non-ICU hospital bed.
- 3.1.3 WHO COVID Scale Score 4 (Oxygen by mask or nasal prongs) or WHO COVID Scale Score 5 (non-invasive ventilation or high-flow oxygen)
- 3.1.4 Age 18 to 90 years old.
- 3.1.5 ECOG performance status ≤ 2 (see Appendix A).
- 3.1.6 Patients receiving or who have received standard of care therapy for COVID-19 can be included. This includes Remdesivir, Dexamethasone (or other steroids), and convalescent plasma.
- 3.1.7 Ability to understand and the willingness to sign a written informed consent document.

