6.2.2.13 Nonsteroidal Anti-inflammatory Drug (NSAID) Interactions: Clinical status and serum creatinine should be closely monitored when cyclosporine is used with NSAIDs in rheumatoid arthritis patients. Pharmacodynamic interactions have been reported to occur between cyclosporine and both naproxen and sulindac, in that concomitant use is associated with additive decreases in renal function, as determined by ^{99m}Tc -diethylenetriaminepentaacetic acid (DTPA) and (p-aminohippuric acid) PAH clearances. Although concomitant administration of diclofenac does not affect blood concentrations of cyclosporine, it has been associated with approximate doubling of diclofenac blood concentrations and occasional reports of reversible decreases in renal function. Consequently, the dose of diclofenac should be in the lower end of the therapeutic range.

6.2.2.14 Methotrexate Interaction: Preliminary data indicate that when methotrexate and cyclosporine were coadministered to rheumatoid arthritis patients (N=20), methotrexate concentrations (AUCs) were increased approximately 30% and the concentrations (AUCs) of its metabolite, 7-hydroxy methotrexate, were decreased by approximately 80%. The clinical significance of this interaction is not known. Cyclosporine concentrations do not appear to have been altered (N=6).

6.2.2.15 Sirolimus: Elevations in serum creatinine were observed in studies using sirolimus in combination with full-dose cyclosporine. This effect is often reversible with cyclosporine dose reduction. Simultaneous coadministration of cyclosporine significantly increases blood levels of sirolimus. To minimize increases in sirolimus concentrations, it is recommended that sirolimus be given 4 hours after cyclosporine administration.

6.2.2.16 Nifedipine: Frequent gingival hyperplasia when nifedipine is given concurrently with cyclosporine has been reported. The concomitant use of nifedipine should be avoided in patients in whom gingival hyperplasia develops as a side effect of cyclosporine.

6.2.2.17 Methylprednisolone: Convulsions when high dose methylprednisolone is given concurrently with cyclosporine have been reported.

6.2.2.18 Other Immunosuppressive Drugs and Agents: Psoriasis patients receiving other immunosuppressive agents or radiation therapy (including PUVA and UVB) should

not receive concurrent cyclosporine because of the possibility of excessive immunosuppression.

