11.5 Analysis of Secondary Endpoints

The secondary objectives are mostly concerned with the safety and effects of Neoral (CSA) in this patient population. The secondary endpoints include Neoral-associated toxicity events, serum inflammatory markers (CRP, d-dimer, ferritin, ANC, absolute lymphocyte count, WBC, PLT (daily while inpatient and including day 14 and 28 for those discharged), Viral load (days 14 and 28), vital status (days 14 and 28), disease improvement (days 14 and 28), proportion of those requiring invasive mechanical ventilation, incidence of deep vein thrombosis, proportion of patients discharged on day 28, time to hospital discharge, and disease resolution (days 14 and 28).

For safety, Neoral-associated toxicity events include nephrotoxicity, resistant hypertension, hepatotoxicity, signs of CNS toxicity, or superinfection. AE's and SAE's by CTCAE v5 will be summarized descriptively with frequencies and rates. Rates and 95% CI's of grade 3 and above AE's will be reported.

Serum inflammatory markers are viewed as interval scales and after appropriate normalizing transformation (if needed), will be analyzed using general linear mixed models to account for within patient dependencies to allow comparisons between groups.

Viral positivity between groups at days 14 and days 28 will be tested by Wilcoxon rank sum test.

Survival analysis methods will be used to describe overall survival experience, to estimate survival at selected time points, and to compare groups. Cumulative incidence analysis methods will be used if there are competing risks. The same approach will be used with disease improvement (alive and free invasive or non-invasive mechanical ventilation) and disease resolution (alive and discharged home without oxygen).

Fisher's exact test will be used to compare rates of need for invasive mechanical ventilation bench marked to a particular time, and ever need. If required, this endpoint will include deaths before intubation in the rare cases in which this occurs.

In exploratory analyses, we will use logistic regression to model ventilator need as a function of treatment group and other baseline characteristics. Survival analysis methods will be used to analyze time to mechanical ventilation, with censoring at last follow-up for those not needing ventilation.

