12. ADVERSE EVENTS: LIST AND REPORTING REQUIREMENTS

Adverse event (AE) monitoring and reporting will be undertaken for 1) Neoral-associated toxicity events including nephrotoxicity, resistant hypertension, hepatotoxicity, signs of CNS toxicity, or new bacterial/mycobacterial infection; as well as 2) other AEs.

Safety duration is at 60 days and we will follow up all AEs and mortality at day 60.

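### Table 4 counts three of the five named Neoral-associated toxicities, so no numerical boundary covers non-fatal grade 3+ superinfection or CNS toxicity

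*Combined protocol and SAP*

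**What the plan says.** Section 11.5 defines the safety events of interest: "Neoral-associated toxicity events include nephrotoxicity, resistant hypertension, hepatotoxicity, signs of CNS toxicity, or superinfection". Section 12 repeats the list with a different infection term: "nephrotoxicity, resistant hypertension, hepatotoxicity, signs of CNS toxicity, or new bacterial/mycobacterial infection".

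Section 11.6.2 sets up continuous monitoring of other expected toxicities, without listing them there. "The method generates a Pocock-type boundary for repeated testing for toxicity", and it "yields the probability of crossing the boundary at most 5% when the rate of grade 3 or greater target toxicity" equals an acceptable 20%. The stated chance of early stopping is 40% at a 30% rate and 86% at a 40% rate. The note to Table 4 names the events to be counted: "Targeted toxicities include renal dysfunction, hypertension and liver toxicity". If the number of patients with a grade 3+ targeted event reaches b_n among n patients followed to Day 7, the trial is paused and the DSMB informed.

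Other safeguards are not limited to these three toxicities. Under 11.6.1, a single death on Neoral judged at least possibly related pauses accrual and prompts DSMB review. Under 11.6.3, the DSMB may recommend closure. Section 12.3 requires reporting of all SAEs to the sponsor and FDA regardless of attribution. Section 13.1 provides for ongoing review by the principal investigator and at least monthly discussion between the two site investigators.

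**The concern.** Two of the five toxicities that the plan attributes to the drug are missing from its only quantitative rule, and the plan does not explain why. Its own text treats both as real hazards. Active bacterial or mycobacterial infection is an exclusion (3.2.5). Low cholesterol is an exclusion because of seizure risk (3.2.10). Tacrolimus is flagged for added immunosuppression and a lower seizure threshold (3.2.11). Section 6.2.2.17 notes: "Convulsions when high dose methylprednisolone is given concurrently with cyclosporine have been reported". Section 3.1.6 admits patients on standard of care: "This includes Remdesivir, Dexamethasone (or other steroids), and convalescent plasma".

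The trial adds an immunosuppressant to treatment that may already contain a steroid, in patients with an active viral infection. A reader of 11.6.2 could take the 5%, 40% and 86% figures as describing protection against Neoral toxicity as a whole. They describe renal, hypertensive and liver events only. A run of non-fatal severe infections or CNS events would leave the Table 4 count unchanged.

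**Working it through.** **Inputs from the documents.** Table 4 boundary b_n for n = 1 to 50 (none at n = 1 and 2; b_3 = 3, b_4 = 4, b_5 = 4, and so on to b_50 = 18); 50 Neoral patients (6.1); acceptable rate 20%; stated crossing probabilities of at most 5%, 40% and 86% at rates of 20%, 30% and 40% (11.6.2).

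**Assumed, because the documents give no figure.** t is the rate of the three counted toxicities and q the rate of grade 3+ infection or CNS toxicity. The two are taken as independent, and each patient counts at most once per tally.

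**Step 1: reproduce the plan's figures.** Let f_n(k) be the probability of k events after n patients with no crossing so far. For k < b_n,

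f_n(k) = (1 − p)·f_{n−1}(k) + p·f_{n−1}(k − 1),

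and any mass at k ≥ b_n is added to the crossing probability. At p = 0.20 the first terms are:

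- n = 3: 0.2³ = 0.0080.
- n = 4: nothing new, since four events in four patients would already have crossed at n = 3.
- n = 5: two events in the first three patients, then two more: 3 × 0.2⁴ × 0.8 = 0.0038.

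Carried through to n = 50:

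| True rate of counted events | Crossing probability | Stated |
|---|---|---|
| 10% | 0.2% | – |
| 15% | 1.1% | – |
| 20% | 4.8% | at most 5% |
| 30% | 39.2% | 40% |
| 40% | 86.4% | 86% |

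The boundary is sound. The issue is only which events enter the count.

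**Step 2: effect of q on Table 4.** Only p = t enters the recursion, so q has no influence. At t = 15% the crossing probability is 1.1% whatever the rate of non-fatal infection or CNS events.

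**Step 3: what the related-death rule can add.** If a share f of the uncounted events is fatal and judged at least possibly related, the chance of at least one such death in 50 patients is 1 − (1 − q·f)^50. With q = 20% (assumed):

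- f = 5%: 1 − 0.99^50 = 39.5%
- f = 10%: 1 − 0.98^50 = 63.6%
- f = 20%: 1 − 0.96^50 = 87.0%

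This route is therefore not negligible, but it responds only to deaths.

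**Step 4: a separate second count against the same b_n.** The table in Step 1 applies with p = q: 0.2% at 10%, 1.1% at 15%, 4.8% at 20%, 39% at 30% and 86% at 40%. If t = q = 20%, the chance that either count crosses is 1 − (1 − 0.048)² = 9.4%, against 4.8% now.

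**Step 5: why not pool all five.** Pooling raises the background rate. With t = 20% and q = 10% the composite is 1 − 0.80 × 0.90 = 28%, which crosses 29.0% of the time. The 20% benchmark would no longer mean what 11.6.2 says it means.

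**The case against.** The strongest reply is that severe infection and CNS toxicity are covered, only not by a number. A fatal case judged possibly related pauses accrual. The DSMB may recommend closure for any reason. Every SAE goes to the sponsor and FDA, and many severe infections or seizures would qualify as life-threatening or as prolonging hospitalization. The investigators review adverse events throughout. The entry exclusions also show these risks being reduced before dosing. On this view, a boundary for selected toxicities with judgement for the rest is a legitimate design choice.

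Much of this stands. A reader might infer that no rate of severe infection or CNS toxicity could ever pause the trial, or that such events would prompt no response at all. The documents do not support that: sections 11.6.1, 11.6.3, 12.3 and 13.1 each provide a route, and Step 3 shows that the death rule can matter. For non-fatal events, however, what remains is judgement with no stated threshold.

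The word *include* in the Table 4 note might be read as leaving the list open. But no further item is named, and a count compared with b_n needs a closed list, so on that reading too the text needs correcting.

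The steroid argument should not be pressed far. Section 6.2.2.17 concerns high-dose methylprednisolone, while 3.1.6 refers only to other steroids in general.

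Finally, reusing b_n carries over a 20% acceptable rate that the documents justify for neither infection nor CNS toxicity. That limits the gain from a second count, which would seldom react to rates of 10% to 15%. It does not remove the gain at higher rates.

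**Conclusion.** The point holds as a gap in numerical coverage. Table 4 counts three of five named toxicities without explanation, and its stated 5%, 40% and 86% do not apply to non-fatal grade 3+ superinfection or CNS toxicity. It does not show that the trial lacks protection against those events, nor that the boundary is miscalculated.

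The size of the gain from closing the gap depends on the true rate of the uncounted events, which the documents do not give. With the printed boundary it is substantial at 30% to 40% and close to nothing at 10% to 15%. The crossing probabilities for each count are exact given a constant event rate and 50 monitored patients. The 9.4% joint figure also needs independence between the two counts. This is a change that should be made, at low cost.

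**What to change.** 1. Reconcile sections 11.5, 11.6.2 with Table 4, and 12 on one toxicity list and one set of terms. Two differences need settling: superinfection (11.5) against new bacterial/mycobacterial infection (12), and hypertension (Table 4) against resistant hypertension (11.5 and 12).

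2. Add to 11.6.2 a separate running count of Neoral patients with grade 3+ CNS toxicity or grade 3+ new infection/superinfection, with the same action as the existing count: pause and report to the DSMB. By default it can use the printed b_n. The sponsor and DSMB should confirm whether a 20% acceptable rate suits these events and, if not, generate a boundary for the rate they choose. State the counting window as well, since Table 4 works to Day 7 while section 12 follows adverse events to day 60.

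3. Keep the existing three-item count and its stated operating characteristics unchanged, and do not pool the five.

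4. If the sponsor prefers to leave these two toxicities to DSMB judgement, say so in 11.6 with the reason, and state that the 5%, 40% and 86% figures apply to the three counted toxicities only.

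The cost is protocol and SAP wording. Adverse events are already assessed daily (11.4.1) and graded by CTCAE v5.0 (12.2). With the printed b_n, the second count adds at most about 5 percentage points to the false-pause chance at a 20% rate, and a crossing leads to a pause and DSMB review, not automatic closure.

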12. ADVERSE EVENTS: LIST AND REPORTING REQUIREMENTS

Adverse event (AE) monitoring and reporting will be undertaken for 1) Neoral-associated toxicity events including nephrotoxicity, resistant hypertension, hepatotoxicity, signs of CNS toxicity, or new bacterial/mycobacterial infection; as well as 2) other AEs.

Safety duration is at 60 days and we will follow up all AEs and mortality at day 60.

12.1 Comprehensive Adverse Events and Potential Risks List(s) (CAEPRs)

12.1.1.1 Adverse Event List(s) for Neoral. For a comprehensive list of adverse events, please see the product insert:
(https://www.accessdata.fda.gov/drugsatfda_docs/label/2019/050715s035,050716s038lbl.pdf).

12.1.1.2 Most Common Adverse Events. Cyclosporine is FDA approved for indications of: 1) Kidney, Liver, and Heart Transplantation 2) Rheumatoid Arthritis, and 3) Psoriasis.

- In Transplant, the principal adverse reactions of cyclosporine therapy are renal dysfunction, tremor, hirsutism, hypertension, and gum hyperplasia.
- In Rheumatoid Arthritis, the principal are renal dysfunction (See WARNINGS), hypertension (See PRECAUTIONS), headache, gastrointestinal disturbances, and hirsutism/hypertrichosis.
- In Psoriasis, principal adverse reactions associated with the use of cyclosporine are renal dysfunction, headache, hypertension, hypertriglyceridemia, hirsutism/hypertrichosis, paresthesia or hyperesthesia, influenza-like symptoms, nausea/vomiting, diarrhea, abdominal discomfort, lethargy, and musculoskeletal or joint pain.

12.1.1.3 Taken together, and based on data from >1000 patients available in the USPI, the most common adverse events of Neoral that may be encountered in this study are: ***Renal dysfunction, hypertension, hirsutism, tremor, headache, nausea, and abdominal pain.***

12.2 Adverse Event Characteristics

- CTCAE term (AE description) and grade:** The descriptions and grading scales found in the revised NCI Common Terminology Criteria for Adverse Events (CTCAE) version 5.0 will be utilized for AE reporting. All appropriate treatment areas should have access to a copy of the CTCAE version 5.0. A copy of the CTCAE version 5.0 can be downloaded from:
http://ctep.cancer.gov/protocolDevelopment/electronic_applications/ctc.htm.
- Attribution** of the AE:
 - Definite – The AE is *clearly related* to the study treatment.
 - Probable – The AE is *likely related* to the study treatment.
 - Possible – The AE *may be related* to the study treatment.
 - Unlikely – The AE is *doubtfully related* to the study treatment.
 - Unrelated – The AE is *clearly NOT related* to the study treatment.

12.3 Expedited Adverse Event Reporting

12.3.1 Expedited Reporting Guidelines

Note: A death on study requires both routine and expedited reporting, regardless of causality as long as the death occurred within 30 days after the last administration of the investigational agent. Attribution to treatment or other cause must be provided.

Expedited Reporting Requirements for Adverse Events that Occur on Studies under an IND/IDE within 30 Days of the Last Administration of the Investigational Agent ¹

FDA REPORTING REQUIREMENTS FOR SERIOUS ADVERSE EVENTS (21 CFR Part 312)

NOTE: Investigators MUST immediately report to the sponsor ANY Serious Adverse Events, whether or not they are considered related to the investigational agent(s)/intervention (21 CFR 312.64). These will be reported to the FDA and to the Sponsor.

An adverse event is considered serious if it results in ANY of the following outcomes:

- 1) Death
- 2) A life-threatening adverse event
- 3) An adverse event that results in inpatient hospitalization or prolongation of existing hospitalization for ≥ 24 hours
- 4) A persistent or significant incapacity or substantial disruption of the ability to conduct normal life functions
- 5) A congenital anomaly/birth defect.
- 6) Important Medical Events (IME) that may not result in death, be life threatening, or require hospitalization may be considered serious when, based upon medical judgment, they may jeopardize the patient or subject and may require medical or surgical intervention to prevent one of the outcomes listed in this definition. (FDA, 21 CFR 312.32; ICH E2A and ICH E6).

ALL SERIOUS adverse events that meet the above criteria **MUST** be immediately reported to the Sponsor via electronic submission within 7 calendar days of learning of the AE.

12.4 Routine Adverse Event Reporting

All Adverse Events must be reported in routine study data submissions.

13. STUDY OVERSIGHT AND DATA REPORTING / REGULATORY REQUIREMENTS

Adverse event lists, guidelines, and instructions for AE reporting can be found in Section 10 (Adverse Events: List and Reporting Requirements).

13.1 Study Oversight

This protocol is monitored at several levels, as described in this section. The Protocol Principal Investigator is responsible for monitoring the conduct and progress of the clinical trial, including the ongoing review of accrual, patient-specific clinical and laboratory data, and routine and serious adverse events; reporting of expedited adverse events; and accumulation of reported adverse events from other trials testing the same drug(s). The Protocol Principal Investigator and statistician have access to the data required for this at all times.

There are 2 sites in this protocol. The lead site is Baylor College of Medicine. The PI from Baylor College of Medicine ([name]) and the PI from the second site, Brigham and Women's

Hospital ([name]) will have a conference at least monthly to review enrollment, AEs, and administrative elements of this protocol.

All Study Investigators at participating sites who register/enroll patients on a given protocol are responsible for timely submission of data via the mechanism described elsewhere in this section. All studies are also reviewed in accordance with the enrolling institution's data safety monitoring plan.

13.2 Data Reporting

13.2.1 Method

Each of the 2 hospital sites will have a dedicated monitor. These individuals, in collaboration with the study monitor, will submit cumulative protocol- and patient-specific data at least every two weeks to a central Encore database. This reporting consists of Patient Demographics, Baseline Abnormalities, On/Off Treatment/Study Status, Treatment/Course/Dosing information, Adverse Events, Late Adverse Events, and Response data as applicable. On-site audits will be conducted two times annually (one annual site visit and one data audit).

13.2.2 Responsibility for Data Submission

It is the responsibility of the PI(s) at the site to ensure that all investigators at both sites understand the procedures for data submission and that protocol specified data are submitted accurately and in a timely manner to the CTMS via the electronic data capture system. Data are to be submitted to this system on a real-time basis, but no less than once every 2 weeks. Metrics for timeliness will be followed and assessed on a quarterly basis. For the purpose of Institutional Performance Monitoring, data will be considered delinquent if it is greater than 4 weeks past due.

